**Figure 3: Trial treatments and concomitant therapies**

Abbreviations: IMP: Investigational medicinal product; PQP: piperaquine; PYR: pyronaridine.

## **6.1      Investigational Medicinal Products (IMPs)**

The following IMPs will be used in this trial:

- piperaquine tetraphosphate – the test IMP
- pyronaridine tetraphosphate – the test IMP
- piperaquine matched placebo – the reference IMP
- pyronaridine matched placebo – the reference IMP.

The following IMP strengths will be used in this trial:

- PYR – 180 mg tablets
- PQP – 320 mg tablets
- PQP matched placebo tablets
- PYR matched placebo tablets.

Bulk IMPs will be supplied and QP certified by MMV or their contractor. Prior to being used on the clinical trial, the IMPs will be prepared by Richmond Pharmacology's clinical trials pharmacy. The prepared individual participant doses will be QP certified and dispensed by the site's pharmacy staff.

PQP is uncoated and bitter to taste, the effect may be persistent for some time after administration. This effect cannot be masked and may provide an indication of the treatment received. As the key safety and tolerability endpoints are objective assessments and parameters, it is anticipated that there will be no impact on the primary trial objective to determine the safety and tolerability of the registered doses of IMP.

### **6.1.1 Packaging and labelling of IMPs**

The labelling of the trial drugs will be in compliance with Good Manufacturing Practice (GMP) specifications, as described in The Rules Governing Medicinal Products in the European Union, Volume 4, Annex 13, Investigational Medicinal Products, and any other or local applicable regulations.

Sample label(s) will be submitted to the UK health authorities according to the submission requirements.

### **6.1.2 Drug administration**

PYR, PQP and matched placebos will be administered orally as detailed in Table 12. Doses of IMP will depend on the participant's body weight. The weight taken on Day -1 should be compared to the weight taken at screening to ensure there is no more than 5 % variation. More details will be provided in the SOM.

**Table 12: IMP or placebo for each anticipated dose level**

Treatment group	Weight (kg)	Treatment:	IMP/Placebo Dispensed:	Administration
1	50 - <65	*PYR 540 mg + PQP 960 mg	Three PYR tablets of 180 mg + three PQP tablets of 320 mg	
	65 - <75	*PYR 720 mg + PQP 960 mg	Four PYR tablets of 180 mg + three PQP tablets of 320 mg	
	≥75	*PYR 720 mg + PQP 1280 mg	Four PYR tablets of 180 mg + four PQP tablets of 320 mg	
2	50 - <65	*PYR 540 mg + placebo for PQP	Three PYR tablets of 180 mg + three placebo PQP tablets	Participants will fast from all food and drink (except for water) for a minimum of three hours prior to dosing.
	65 - <75	*PYR 720 mg + placebo for PQP	Four PYR tablets of 180 mg + three placebo PQP tablets	
	≥75	PYR 720 mg + placebo for PQP	Four PYR tablets of 180 mg + four placebo PQP tablets	
3	50 - <65	*placebo for PYR + PQP 960 mg	Three placebo PYR tablets + three PQP tablets of 320 mg	Participants may drink water until one hour prior to dosing, and from one hour after dosing.
	65 - <75	placebo for PYR + PQP 960 mg	Four placebo PYR tablets + three PQP tablets of 320 mg	
	≥75	*placebo for PYR + PQP 1280 mg	Four placebo PYR tablets + four PQP tablets of 320 mg	
4	50 - <65	placebo for PYR + placebo for PQP	Three placebo PYR tablets + three placebo PQP tablets	IMPs will be administered to each participant with approximately 240 mL of water.
	65 - <75	placebo for PYR + placebo for PQP	Four placebo PYR tablets + three placebo PQP tablets	
	≥75	placebo for PYR + placebo for PQP	Four placebo PYR tablets + four placebo PQP tablets	

Abbreviations: IMP: investigational medicinal product; mL: millilitres; PQP: piperaquine; PYR: pyronaridine.

\*Efforts will be made to recruit participants in order to stratify randomisation according to weight, so that a minimum of two participants receive each of the seven treatment options, i.e. ≥ two participants will be administered with each of the following treatment options:

- PYR 540 mg + PQP 960 mg
- PYR 720 mg + PQP 960 mg
- PYR 720 mg + PQP 1280 mg
- PYR 540 mg + placebo for PQP
- PYR 720 mg + placebo for PQP
- placebo for PYR + PQP 960 mg
- placebo for PYR + PQP 1280 mg.

An RP will verify doses of PYR, PQP or matched placebo(s) and the details of dosing will be recorded in the CRF. The dosing will be verified by another member of the Investigator's staff. Detailed instructions for dose administration will be included in the SOM.

---

In the event that a participant vomits following IMP administration on a particular dosing day, that participant will not be re-dosed on that same day, however they will receive IMP on the subsequent days as planned (as per Table 5: Schedule of Assessments). The exact time of vomiting will be documented in the source document and eCRF for PK analysis purposes (i.e. to refine sub-populations depending on the time of vomiting).

### **6.1.3 Storage of IMPs**

PYR, PQP and matched placebos will be stored in accordance with the labelling instructions as defined in the IMPD. The IMPs will be stored securely in a temperature-controlled pharmacy with authorised access only.

### **6.1.4 Drug accountability**

The designated pharmacy staff at the clinical trial site will maintain accurate records of the receipt and the condition of all trial IMP including dates of receipt. In addition, accurate records will be kept by the pharmacy staff of when and how much trial IMP is dispensed and used by each participant in the trial. Any reason for departure from the protocol dispensing regimen must also be recorded.

IMP accountability records and inventory will be available for verification by the Sponsor or designee. At the completion of the trial, there will be a final reconciliation of all trial IMPs.

A trial IMP must not be used for any purpose other than the present trial. The destruction of remaining trial IMP will be arranged by the clinical trial site according to applicable regulations and only after receipt of written authorisation from the Sponsor.

## **6.2 Treatment allocation and blinding**

### **6.2.1 Participant randomisation**

All participants in this trial will be assigned to a treatment regimen according to a randomisation schedule generated by a statistician using PROC Plan. Details regarding the unique screening and participant number will be included in the SOM.

Eligible participants will be randomly assigned in a 2:1:1:1 ratio to one of four treatment arms on Day 1, at the point of dosing. Treatment arms are outlined below:

- Treatment 1 (N=16): PYR + PQP
- Treatment 2 (N=8) : PYR + placebo for PQP
- Treatment 3 (N=8) : placebo for PYR + PQP
- Treatment 4 (N=8) : placebo for PYR + placebo for PQP.

Sentinel dosing (N=10) will occur: four participants for treatment arm 1, and two participants from each of treatment arms 2, 3 and 4, will be dosed before the remaining participants of each treatment arm are dosed together (see Section 3.4.4).

### **6.2.2 Methods for ensuring blinding**

The trial will take place in a double-blind fashion whereby participants and clinical trial site staff are blinded to the active or placebo trial drug assignment.

PQP is uncoated and bitter to taste, the effect may be persistent for some time after administration. This effect can not be masked and may provide an indication of the treatment received. As the key safety and tolerability endpoints are objective assessments and parameters, it is anticipated that there will be no impact on the primary trial objective to determine the safety and tolerability of the registered doses of IMP.

The pharmacy staff preparing the investigational products will not be blinded to trial drug assignment. During the trial, the individual randomisation codes will be kept in the site's clinical trials pharmacy, accessible to the pharmacy personnel only. Upon completion of the trial, after the database lock and after the blind is revealed, the randomisation list will be filed in the Trial Master File (TMF).

Sponsor staff involved in clinical decision-making (such as those involved in SRC decisions) will be blinded to trial drug assignment (see AR rules section above).

### **6.2.3 Methods for unblinding the trial**

In the event of an emergency, an envelope for each participant containing his/her trial drug assignment will be available in the pharmacy at the clinical trial site. Unblinding should only be considered for the safety of the participant. If unblinding is deemed necessary by the Investigator, the Investigator or designee can unblind the participant's treatment allocation using the envelope available from the pharmacy. The Investigator or designee must note the date, time and reason for unblinding and inform the sponsor of unblinding as soon as practicably possible.

If there is an unblinding, the randomisation schedule should be revised and this should be communicated to the RPL pharmacy team. Unblinding if required will be done in accordance with RPL SOP. SRC can decide whether to unblind a participant in either an emergency or non-emergency fashion.

## **6.3 Concomitant medications/permited medications**

The use of hormonal contraception and hormone replacement therapy is permitted. During the trial, other prescription or over-the-counter medications may be permitted at the discretion of the Investigator. The need for other medication may lead to participant's withdrawal from the trial. In any case, the Investigator will inform the sponsor about the concurrent medication given.

Ibuprofen/NSAIDS should be used for rescue pain relief only, at the discretion of the PI. The dose and reason for ibuprofen/NSAID use in AEs other than as rescue medication must be recorded in the CRF and source record.

Details of all other prior and concomitant medications should be recorded by the Investigator on the CRF and source record.

## **6.4 COVID-19 vaccinations**

Given the current COVID-19 pandemic, consideration has been made regarding participants who have had the vaccination or may be offered the vaccination during trial participation (see Section 5.4).

To optimise the data collected from this trial, the following rules will apply.

Participants may not be considered for participation if they:

- have received a COVID-19 vaccination within the four weeks prior to Day 1 of the trial
- plan to receive a vaccination from one week after trial completion/last visit.

## **7. TRIAL METHODOLOGY**

### **7.1 Medical history**

All clinically significant medical history (including any significant surgical procedures) must be recorded on the CRF for each participant. Each participant's full medical history will be obtained through direct questioning and the medical assessment at screening and will be updated at the day of admission (Day -1). If any clinically relevant observations or investigation results are detected prior to dosing, they will be recorded as medical history.

### **7.2 Eligibility check**

The RP will perform a trial eligibility check for all trial participants during the screening period and on Day -1, as described in the Schedule of Assessments (Table 5 and Table 6). Further details will be provided in the SOM.

### **7.3 Prior and concomitant medication check**

Each participant will have a prior and concomitant medication check as described in the Schedule of Assessments (Table 5 and Table 6) and in Section 0.

### **7.4 Beck depression inventory**

Each participant will undergo a Beck Depression Inventory questionnaire [26], as described in the Schedule of Assessments (Table 5 and Table 6). A participant will be excluded from the trial if they have a score of 20 or more on the Beck Depression Inventory, and/or a response of 1, 2 or 3 for item 9 of this inventory (related to suicidal ideation) [26].

### **7.5 Meals**

Standardised meals will be provided during the trial period according to the timings described in the Schedule of Assessments (Table 5 and Table 6).

On dosing days, participants will fast of all food and drink (except water) for at least three hours prior to IMP administration and for at least four hours post-dose.

Participants can drink water until one hour pre-dose and from one hour post-dose.  
Meals on the discharge day are optional.

## 7.6 Clinical laboratory assessments

Laboratory parameters to be measured are presented in Table 13.

**Table 13: Laboratory parameters**

Haematology	Biochemistry	Urinalysis	

Platelets

Hb

Haematocrit

White blood cells

Neutrophils

Eosinophils

Basophils

Lymphocytes

Monocytes

Red blood cells

Mean cell haemoglobin (MCH)

Mean corpuscular haemoglobin concentration (MCHC)

Mean corpuscular volume (MCV)

HbA1c***

	

Aspartate aminotransferase (AST)

Alanine aminotransferase (ALT)

Alkaline phosphatase (ALP)

BUN

Gamma GT

Total bilirubin

Direct bilirubin

Indirect bilirubin

Creatinine

Urea

Total Serum Proteins

Albumin

Alpha1 Glycoprotein#

Sodium

Potassium

Calcium

Corrected calcium

Magnesium

Chloride

Bicarbonate

Amylase

Total cholesterol

Triglycerides

Serum pregnancy test*

FSH*

	

Leukocytes

Nitrite

Urobilinogen

Protein

pH

Blood

Specific gravity

Ketones

Bilirubin

Glucose

Urine microscopy**

	
Coagulation			

aPTT

PT

Fibrinogen

INR

	

Amylase

	Urine Screen for Drugs of Abuse	
Serology			

Hepatitis B surface Antigen (HBsAg)

Hepatitis B core Antibody (anti-HBC IgG + IgM, if IgG positive)

Hepatitis C Antibody (anti-HCV)

HIV I and II Antibodies

	

Total cholesterol

Triglycerides

Serum pregnancy test*

FSH*

	

Benzodiazepines

Opiates

Amphetamines

Methamphetamines

Methadone

Cocaine

Cannabinoids

Barbiturates

Phencyclidine

Tricyclic antidepressants

	

\* Measured at the times presented in the Schedule of Assessments (Table 5 and Table 6). Serum pregnancy test for pre-menopausal women only; FSH for post-menopausal women only. \*\* Only if urinalysis is abnormal. \*\*\* Measured at screening only. # On admission day only.

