Other most frequently reported AEs (>1/100 to <1/10) are headache, eosinophilia, neutropenia, anaemia, increased platelet count, vomiting (2.2 to 2.5 %), abdominal pain, bradycardia, transaminase increases and hypoglycaemia [18]. Additionally, analyses performed in malaria patients suggest that no clinically concerning QTc prolongation is expected at therapeutic concentrations of PYR [10].

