4. See Table 13 for details of laboratory parameters to be measured.
5. Plasma samples for PQP and blood samples for PYR. See Table 6 for time-points.
6. Continuous 12-lead telemetry will be recorded from at least one hour pre-dose on Day 1 to 24 hours post-dose on Day 3.
7. Update only on Medical History at admission.
8. On Day -1, only weight will be collected and height from screening will be used for BMI calculation.
9. Standard meals will be served at standard unit times. On Days 1, 2 and 3 the first meal will be lunch given four hours post-dose. Meals will be optional on the discharge day.
10. Dosing will be carried out in fasted state on the morning of each dosing day (Days 1, 2 and 3), firstly with PYR/ placebo tablets, followed by PQP/ placebo tablets.
11. Participants in the sentinel group will remain in-house until Day 7. If there are no clinically concerning safety signals, the remaining participants subsequently dosed (from the main group) will remain in-house until Day 5.
12. On Day 2 and Day 3, only the following safety blood tests will be measured: AST, ALT, bilirubin.

Note: COVID-19 tests will be carried out at regular intervals, prior to entry in the unit and throughout the residential period as per the latest RPL COVID-19 Infection Control Guidelines and pre-entry algorithms.

Abbreviations: AE: Adverse Event; BMI: body mass index; D: Day (where Day 1 is the first day that IMPs are administered); ECG: electrocardiogram; FSH: Follicular Stimulating Hormone; PK: pharmacokinetic; PQP: piperaquine; PYR: pyronaridine.

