**Table 6 Schedule of Assessments (continued)**

Trial Day	Time (h)	PK sampling 	12-lead ECG 	Vitals 	Meals 
D1	-1.5		X		
	-1		X		
	-30 mins	X	X	X	
	1	X	X	X	
	2	X	X	X	
	3	X	X		
	4	X	X		X
	5	X	X	X	
	6	X	X		
	7	X	X		
	8	X	X	X	
	10				X
	12	X	X		X
D2	-1.5		X		
	-1		X		
	-30 mins	X	X	X	
	4	X	X	X	X
	6	X	X	X	
	10				X
	12	X	X	X	X
D3	-1.5		X		
	-1		X		
	-30 mins	X	X	X	
	-5 mins		X		
	1	X	X	X	
	2	X	X	X	
	3	X	X		
	4	X	X		X
	5	X	X	X	
	6	X	X		
	7	X	X		
	8	X	X	X	
	10				X
	12	X	X		X

1. Plasma samples for PQP and blood samples for PYR.
2. 12-lead ECG will be measured in triplicate after a rest period of at least ten minutes in supine position.
3. Vital signs will be measured after rest of at least five minutes in supine position. Standing vitals will be performed after one minute in the upright standing position, to assess for orthostatic change, on Screening, Day -1, and on Day 1 and Day 3 at pre-dose (-30 min) and post dose at 5h.
4. On dosing days, participants will fast from all food and drink (excluding water) at least three hours pre-dose and four hours post-dose. Participants may drink water until one hour before dosing and may re-commence water one hour subsequent to dosing.
5. Four-hour procedures to be completed prior to lunch being given

Abbreviations: D: day; ECG: electrocardiogram; h: hours (where hour 0 is the time at which the first IMP is administered); mins: minutes; PK: pharmacokinetic.

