Samples and Assessments (safety)	
7. Additional safety assessments may be performed on an individual participant if it is considered clinically necessary by the PI for individuals on a case-by-case basis.
 
8. Additional safety assessments (including but not limited to laboratory safety samples, vital signs and ECGs) may be added to the Schedule of Assessments at additional time-points for an upcoming treatment arm if the SRC considers it necessary from a safety/tolerability perspective, on the basis of evolving data.
 
9. Additional safety assessments may refer to either:
 
 
a. an increased number of the same safety assessments planned in the existing Schedule of Assessments.
 
b. additional parameters (specific tests) on assessments already scheduled e.g. troponin tests on safety blood samples.
 
c. additional safety tests requiring additional blood/urine sample collections or other clinical
 
	
I. Trial specific maximum blood volume (470 ml) will not be exceeded (Section 7.12).
 
II. A maximum for individuals will be determined on a case-by-case basis and cannot be pre-defined, because investigations will be performed as necessary to ensure the safety of the individual participants.
 
III. If additional safety assessments or parameters are required for upcoming treatment arms/cohorts and have a similar risk profile to those planned in this trial protocol, they will be documented in a non-substantial amendment. Additional safety assessments required for upcoming treatment arms/cohorts that are more invasive or have a different risk profile to those in this current protocol must be detailed in a substantial amendment.

Adaptive Study Design Areas	Features	Limits
	
procedures e.g. ultrasound scans.
 
10. Specialist referrals (e.g. to a cardiologist) may be made (and may include all relevant assessments and investigations) if it is considered clinically necessary by the PI or Sponsor or SRC for individuals on a case-by-case basis.
 
11. The timing of safety assessments including but not limited to laboratory safety samples, vital signs and ECGs may be adjusted in accordance with evolving data and dosing schedule.
	
IV. Alterations in timing of the safety assessments need to be a reflection of the established safety/tolerability and PK profile up to the decision-making time-point.

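### Hypoglycaemia is listed as a frequent pyronaridine adverse event, but no scheduled test measures blood glucose, so asymptomatic falls would go unseen in every arm

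*Protocol*

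**What the plan says.** **Risk text.** Protocol Section 1.2.2.2 opens its list of PYR events with "Other most frequently reported AEs (>1/100 to <1/10) are headache, eosinophilia" and closes it with "abdominal pain, bradycardia, transaminase increases and hypoglycaemia". The safety and tolerability part of Section 1 gives the same list and frequency band.

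**Fasting.** Section 7.5 requires participants to fast "for at least three hours prior to IMP administration and for at least four hours post-dose" on each dosing day (Days 1, 2 and 3).

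**Laboratory panel.** Section 7.6 makes Table 13 the list of laboratory parameters. Its biochemistry column contains "Bicarbonate Amylase Total cholesterol Triglycerides" among other items, but no blood, serum or plasma glucose. Glucose appears only under urinalysis. HbA1c appears under haematology and is marked as a screening test.

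**Dosing days.** Footnote 12 to Table 5 reads "On Day 2 and Day 3, only the following safety blood tests will be measured: AST, ALT, bilirubin".

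**Flexibility.** Table 7 (items 7 to 9) allows extra safety assessments for an individual, or for an upcoming arm if the Safety Review Committee (SRC) thinks them necessary. These include "additional parameters (specific tests) on assessments already scheduled". It schedules none.

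**Endpoint and analysis.** Section 2.2.1 makes the proportion of participants with clinically significant changes in safety laboratory tests, biochemistry included, a primary endpoint. SAP Section 4.11.2 summarises the laboratory parameters. Its grading table covers ALT, AST and total bilirubin, and it mentions no glucose analysis.

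**The concern.** The protocol names a laboratory-defined event as frequent with one of its two drugs, then sets a panel that cannot show it. The other laboratory abnormalities in the same list all have their analyte in Table 13: eosinophils, neutrophils, haemoglobin, platelets and transaminases. No reason is given for leaving glucose out.

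The trial's primary objective is safety of each drug alone and in combination against placebo, and Section 1.1 calls it the first human study of the combination. If glucose is never measured on schedule, a report with no laboratory hypoglycaemia could be read as evidence that none occurred, when for asymptomatic cases it means only that nobody looked. The comparison with placebo that the design makes possible would not be available for this event.

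**Working it through.** **1. Could any scheduled item show a low blood glucose after dosing?**

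| Item | Where | Shows an acute fall? |
|---|---|---|
| Biochemistry panel | Table 13 | No: glucose not listed |
| Urine glucose | Table 13, urinalysis | No: does not show a low blood value |
| HbA1c | Table 13, screening only | No: taken before dosing and not a measure of acute change |
| Day 2 and Day 3 bloods | Table 5, footnote 12 | No: AST, ALT and bilirubin only |
| Adverse reaction rules | Tables 9 and 10 | No glucose criterion |
| Adverse events of special interest | Section 8.2.5 | Hepatic, cardiac and haematological only |
| Risk tables | Tables 2 and 3 | Hypoglycaemia not mentioned |
| SAP laboratory analysis | SAP 4.11.2 | No glucose analysis |

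In the text version of Table 13 some biochemistry items appear twice, but neither run includes glucose.

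**2. Length of the fast.** 3 h + 4 h = at least 7 h around each dose. Section 1 puts the PYR peak at two to eight hours after dosing, so the end of the fast falls inside the peak window.

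**3. The plan's own detection figure.** Section 10.7 uses P(at least one case) = 1 − (1 − p)^n with n = 16.

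- p = 0.10: 1 − 0.90^16 = 0.815 (stated 81%)
- p = 0.20: 1 − 0.80^16 = 0.972 (stated 97%)

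Both are reproduced.

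**4. The same formula over the listed band.** The planned number exposed to PYR is 16 + 8 = 24.

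| Rate p | n = 16 (combination) | n = 24 (all PYR) | Expected cases in 24 (24 × p) |
|---|---|---|---|
| 1% | 14.9% | 21.4% | 0.24 |
| 5% | 56.0% | 70.8% | 1.2 |
| 10% | 81.5% | 92.0% | 2.4 |

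These are chances that a case occurs and is recognised. They apply in full only if every case, symptomatic or not, can be found.

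**5. Effect of the smaller enrolment.** SAP Section 3.2 says recruitment stopped at 37, three below plan, without giving the split by arm. In the worst case for this question all three are missing from the combination arm, leaving 13 there and 21 on PYR. The ranges become 1 − 0.99^13 = 12% to 1 − 0.90^13 = 75%, and 1 − 0.99^21 = 19% to 1 − 0.90^21 = 89%. The conclusion does not change.

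**6. What scheduled tests add for asymptomatic cases.** Nothing, in any arm and at any p. The documents do not give the proportion of cases that are asymptomatic, so the number missed cannot be computed.

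**The case against.** The strongest reply has five parts.

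- **The rate may not transfer.** The documents call hypoglycaemia an adverse event, not a reaction, and do not say whether the band comes from patients or healthy participants. The PYR programme described in Section 1.2.2.2 used PYR with artesunate, and the source cited there is unpublished sponsor material. For bradycardia, an item in the same list, Table 3 itself links the falling heart rate to resolving malarial fever. This stands: applying 1–10% to healthy adults on PYR alone or with piperaquine (PQP) is an assumption.
- **The trial is not blind to hypoglycaemia.** A reader might infer that the count must be zero in all arms. The documents do not support that. Symptomatic cases would be captured as treatment-emergent adverse events, also a primary endpoint, and Table 7 lets the investigator order a test. In addition, the laboratory endpoint counts clinically significant changes, so a single incidental low value would not automatically count. This stands and limits the point to asymptomatic falls.
- **No additive effect is documented.** A reader might also infer that PQP would add to the risk, or that this fast raises it. Section 1 gives the overlapping events as, for example, nausea, vomiting, diarrhoea, dizziness and AST/ALT increases, and does not attribute hypoglycaemia to PQP. No passage links the fast to hypoglycaemia with PYR. Neither inference is used here.
- **The panel follows stated priorities.** Section 1 names gastrointestinal, liver and QTc toxicity as the focus, and the protocol never promises glucose testing. That explains where the special rules sit. It does not explain leaving out the analyte for one listed event while measuring amylase, cholesterol and triglycerides.
- **Extra tubes may not fit.** Section 7.12 caps blood volume at 470 mL and gives no running total, so the headroom cannot be checked. This stands for new samples, but has little force for one more analyte on biochemistry already drawn.

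**Conclusion.** The gap is real but narrow. Hypoglycaemia is listed as a frequent PYR adverse event, dosing takes place within a fast of at least 7 hours, and no scheduled assessment measures blood glucose. Asymptomatic falls cannot be seen on schedule in any arm, so the biochemistry part of the primary endpoint carries no information on them.

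The 15–81% (16 on the combination) and 21–92% (24 on PYR) chances of at least one case rest on three things: the listed band applying to healthy adults without artesunate, the planned arm sizes, and complete detection. They show that a case is plausible in a trial of this size. They do not estimate how many would be missed. It would go too far to say that the trial cannot detect hypoglycaemia at all, or that a combination effect is expected.

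**What to change.** - Add serum or plasma glucose to the Table 13 biochemistry panel for all draws already scheduled, and add it to the reduced Day 2 and Day 3 set in footnote 12. Changing Table 13 alone would leave those two dosing days uncovered.
- State when the Day 1 to Day 3 safety bloods are taken relative to dose. Table 6 gives times for PK, ECG, vital signs and meals but not for safety bloods, and the timing decides what a glucose value can show.
- Summarise glucose with the other laboratory parameters under SAP Section 4.11.2, with its reference range and grading.
- Optional: one further glucose sample at the existing 4-hour PK draw on dosing days, which Table 6 already places before lunch, once the 470 mL cap has been confirmed.
- If dosing is already complete, state in the clinical study report that blood glucose was not assessed, so that absence of laboratory hypoglycaemia is not read as evidence of no effect.

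**Cost.** Slightly more laboratory expense for one analyte on samples already drawn, and possibly a small extra blood volume. Table 7 already foresees added parameters, and for upcoming arms or cohorts it handles additions of similar risk by non-substantial amendment. No dose, fasting rule or stopping rule is affected.
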